4.9 Statistical Methods

4.9.1 Sample Size

Up to 24 healthy subjects will be enrolled (including 4 potential replacement subjects). The number of subjects was determined to have greater than 80% power for comparisons between treatment arms across prespecified consecutive timepoints (different timepoints for each comparison). These power calculations are based on 18 subjects with each comparison, allowing for potential dropouts. These analyses adjust for multiplicity using Pocock boundaries for assessing the same endpoint at multiple timepoints. Coefficient of variations and effects sizes for different treatment scenarios were determined using modeling and simulation from previous naloxone studies.

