4.4 Sample Size

Twenty healthy participants are planned for enrollment with up to 4 replacements. Naloxone plasma concentration profiles and variabilities were calculated based on summary pharmacokinetic data from the IN naloxone product label. Predicted naloxone concentrations were determined for each of the proposed dosing treatments based on principles of superposition (i.e., for linear pharmacokinetics the total concentration of a drug in circulation is the sum of remaining concentration from each administered dose prior to the current measurement time) with a focus on comparing plasma concentrations at early timepoints. Power calculations were based on the ratio between concentrations for each of the two primary comparisons (Treatment A vs Treatment C and Treatment B vs Treatment C). Of the comparisons, the power for the 4-dose naloxone arm A (test) versus the 2-dose naloxone arm C (reference) was expected to be lower than the 4-dose naloxone arm B (test) versus the 2-dose naloxone arm C (reference). For the different proposed treatments, the ratio in concentrations and the coefficient of variation (CV) at each timepoint based on principles of superposition are shown in Table 4-1.

Table 4-1: Predicted concentration ratio and CV between treatments at different timepoints and power calculation at a 0.0221 significance level

Comparison	Time (min)	Concentration Ratio	CV	Power (n=18) at $p = 0.0221$
Primary Endpoint (comparisons of 4-dose treatment arms vs. 2-dose treatment arm reference)				
Treatment A vs Treatment C	10	1.36	68	49
	12.5	1.57	58	91
	15	1.78	48	100
Treatment B vs Treatment C	4.5	2	111	86
	7	2	90	94
	10	2	68	99
Secondary Endpoint (comparison between the 4-dose treatment arms)				
Treatment B vs Treatment A	4.5	2	111	86
	7	1.85	90	88
	10	1.47	68	68

As the intent of administering naloxone is rapid reversal of an overdose, the planned primary analysis is a comparison of naloxone concentrations between treatment arms across pre-specified consecutive time points. Each of the paired comparisons was assumed to include three pre-specified timepoints (timepoints correspond to those listed in Table 4-1). The time points will be evaluated sequentially with adjustments for multiplicity using Pocock boundaries (Pocock, 1977). For three pre-specified assessments, this would correspond to assessments at a 0.0221 significance level for comparisons at individual time points to maintain an overall 0.05 significance level.

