Based on these considerations and the concentration ratios and CVs in Table 4-1, a sample size was determined so that at least one of the planned time points would have greater than 90% power at a 0.0221 significance level for a one sided, log-transformed paired comparison (for the primary endpoint). For concluding an increase in naloxone concentration for Treatment A compared to Treatment C at 15 minutes, at least 12 subjects would be necessary assuming a 1.78-fold increase in exposure and 48% CV for the treatments. For concluding an increase in naloxone concentration for Treatment B compared to Treatment C at 10 minutes, at least 12 subjects would have the desired power assuming a 2-fold increase in exposure and 68% CV for the treatments. The sample size was further increased to 20 subjects to account for discontinuations and situations where the CV values in Table 4-1 may be underestimated for repeat naloxone dosing.

5. Analysis Populations

The PK population will include all subjects who receive study drug and have at least one estimable PK parameter after dosing. The safety population will include all subjects who receive

at least 1 dose of the study drug. The analysis population will include all subjects in the PK population with sufficient data to calculate PK parameters. Only subjects with results from two or more periods will be included in comparisons. Treatment in all analysis populations will be assigned based upon the treatment which the subjects actually received.

6. Data Screening and Acceptance

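### Does Table 4-1 overstate power by using a per-treatment CV as the SD of a paired difference?

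*SAP*

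**What the plan says.** SAP 4.4 sizes the trial on "greater than 90% power at a 0.0221 significance level for a one sided, log-transformed paired comparison", to be met at one or more of the three planned timepoints of each primary comparison. Table 4-1 lists a predicted concentration ratio, a CV and a power for each of nine comparison-by-time rows. Protocol 4.9.1 confirms the base: "These power calculations are based on 18 subjects with each comparison".

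The CV is described in several ways:

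- The table caption reads "Predicted concentration ratio and CV between treatments at different timepoints and power calculation at a 0.0221 significance level", which can be taken to mean the variability of the comparison.
- The text on A vs C at 15 minutes says "at least 12 subjects would be necessary assuming a 1.78-fold increase in exposure and 48% CV for the treatments", and the sentence on B vs C at 10 minutes uses the same phrase with 68%. That suggests the variability of concentrations within a treatment.
- On the source, the SAP says "Naloxone plasma concentration profiles and variabilities were calculated based on summary pharmacokinetic data from the IN naloxone product label". The protocol says "Coefficient of variations and effects sizes for different treatment scenarios were determined using modeling and simulation from previous naloxone studies".

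Neither document names the CV as total, within-subject or of the paired ratio. Neither gives a correlation between a subject's concentrations under two treatments. The SAP says that enrolment was raised to 20 to cover discontinuations and "situations where the CV values in Table 4-1 may be underestimated for repeat naloxone dosing".

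**The concern.** A paired test depends on the spread of the within-subject difference, not on the spread of each treatment's values. With a per-treatment CV, the two are linked by the within-subject correlation. Leaving that step out amounts to assuming a correlation of 0.5.

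There are good reasons to suspect that this happened. The text speaks of the CV for the treatments. The CVs come from summary product data. They also vary with time only: 68% at 10 minutes in all three comparisons, although the predicted ratios there are 1.36, 2 and 1.47.

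The endpoint makes early power matter, because it is the first timepoint that passes. For B vs C the predicted ratio is 2 at 4.5, 7 and 10 minutes, so under the plan's own model a miss at 4.5 minutes reflects power alone. The chance of that miss is 14% as stated (100 − 86). It would be 43% at zero correlation and 1% at 0.75. The two statements that 12 subjects suffice are exposed in the same way.

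**Working it through.** **Inputs.** From SAP 4.4: ratios and CVs in Table 4-1, one-sided significance level 0.0221 per timepoint, log scale, paired comparison. From Table 4-1 and Protocol 4.9.1: n = 18.

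**Step 1: reproduce the table.** Take SD_diff = sqrt(ln(1 + CV²)) and noncentrality = ln(ratio) × sqrt(n) / SD_diff. Power is the probability that a noncentral t with n − 1 degrees of freedom exceeds the one-sided critical value (2.173 for 17 degrees of freedom).

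Example, B vs C at 4.5 minutes: SD_diff = sqrt(ln(1 + 1.11²)) = 0.896. Noncentrality = 0.693 × 4.243 / 0.896 = 3.28. Power = 85.8%; the SAP states 86.

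| Comparison | Times (min) | Recomputed power (%) | Stated (%) |
|---|---|---|---|
| A vs C | 10 / 12.5 / 15 | 49.1 / 90.7 / 99.9 | 49 / 91 / 100 |
| B vs C | 4.5 / 7 / 10 | 85.8 / 94.2 / 99.3 | 86 / 94 / 99 |
| B vs A | 4.5 / 7 / 10 | 85.8 / 87.9 / 68.4 | 86 / 88 / 68 |

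All nine agree. The log-normal conversion was applied: the unconverted CV used as the SD gives 68% for B vs C at 4.5 minutes, not 86%. At n = 12 this formula gives 97% (A vs C, 15 minutes) and 93% (B vs C, 10 minutes), so the two sentences on 12 subjects also meet the 90% target.

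**Step 2: what the formula assumes.** If the CV is that of the paired ratio, nothing further is needed. If it is per-treatment, with equal log-scale variance in both treatments and log-scale correlation ρ, then SD_diff = sqrt(2(1 − ρ)) × sqrt(ln(1 + CV²)). The first factor equals 1 only at ρ = 0.5. If the CV is purely within-subject, the factor is sqrt(2), the same as ρ = 0.

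**Step 3: power at n = 18 across ρ (%).** Times are in the same order as above.

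| ρ | A vs C | B vs C | B vs A |
|---|---|---|---|
| 0 | 27 / 64 / 94 | 57 / 70 / 88 | 57 / 60 / 40 |
| 0.25 | 35 / 76 / 98 | 69 / 82 / 95 | 69 / 72 / 51 |
| 0.5 (equals Table 4-1) | 49 / 91 / 100 | 86 / 94 / 99 | 86 / 88 / 68 |
| 0.75 | 79 / 100 / 100 | 99 / 100 / 100 | 99 / 99 / 93 |

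**Step 4: compare with the plan's own criteria.**

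- *SAP target, above 90% at one or more timepoints of each primary comparison.* A vs C meets it at every ρ shown. B vs C meets it from ρ of about 0.08 upward at n = 18. At ρ = 0 it has 88% with 18 evaluable pairs, 89.5% with 19 and 91% with 20.
- *Protocol claim, above 80% across the planned timepoints.* Testing succeeds if any of the three timepoints passes, so overall power is no lower than the best single row. For the primary comparisons that is 94% and 88% or more, even at ρ = 0.
- *Twelve subjects.* At ρ = 0 the powers are 79% and 69%. Reaching 90% needs ρ of about 0.28 (A vs C) and 0.43 (B vs C).

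**The case for a change.** The case for a change is that a reader cannot verify the stated powers without knowing the CV type. On the per-treatment reading, several of them depend on an undisclosed value of 0.5. The 12-subject statements fail at low correlation. For B vs A, no single timepoint reaches 80% at n = 18 unless ρ is at least 0.38. The rise to 20 was justified by dropout and understated CVs, not by correlation, so it cannot simply be credited against this.

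Much of that stands. The assumption is unstated, the wording favours a per-treatment CV, and 20 enrolled is not the same as 20 evaluable pairs. Three things limit it.

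- The per-treatment reading is not certain, because the caption speaks of CV between treatments. One CV per timepoint does not settle the matter. Under superposition, at 10 minutes arm A carries doses given at 5 and 7.5 minutes that arm C lacks, so true per-treatment CVs need not be equal either. A single value per time is a simplification on both readings.
- The B vs A shortfall is smaller than single rows suggest, since success at any of three timepoints counts. In a simulation assuming correlation of 0.5 to 0.8 between timepoints, overall power at n = 18 was 81–88% at ρ = 0.25 and 70–79% at ρ = 0. Some shortfall therefore remains at very low correlation, for a secondary comparison.
- Zero correlation is an extreme case if the CVs include between-subject variation. That would be usual for summary product data but cannot be confirmed here. A purely within-subject CV would give the ρ = 0 row.

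**Conclusion.** The concern is right about how the table was calculated but does not show that any stated figure is wrong. The powers are correct for a paired-ratio CV, and also for a per-treatment CV with equal log variances and a correlation of 0.5. The direction of any error is unknown.

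The consequence is confined to planning figures. The primary design target holds at 18 evaluable subjects for any correlation of about 0.08 or more. At zero it is missed only for B vs C, at 88% against 90%. The powers most sensitive to the assumption are those at early timepoints, those for B vs A and those at 12 subjects, but 12 is not the number enrolled.

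The paired t-test in SAP 7.3.1 uses the observed differences, so neither its validity nor its result depends on what was assumed at planning. Naming the CV type would help a reader check the table. It would leave enrolment, data collection, the test and its thresholds unchanged. This is a gap in documentation, and no change to the plan follows.

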6.1 Handling of Missing and Incomplete Data

The following approaches will be used for the handling of missing and incomplete data:

- Missing PK data (e.g., skipped plasma sample collected) will not be imputed.
- Missed dose, dose administered outside the window, or other issues with dose administration (e.g., product delivery fails) will result in PK data from that period for that subject being excluded from all treatment arm comparisons and summary statistics from that time point forward. Other situations, such as a subject sneezing in close proximity to dosing will be carefully documented by study staff and handling of these cases will be determined and documented before any concentration data is available.
- PK samples collected outside the protocol-defined sampling window (i.e., more than \pm 0.5 minute from the scheduled time for the first 15 minutes of collections) will be excluded from analyses comparing naloxone concentrations at the specific time point that is outside the window.
- PK measurements below the lower limit of quantification will be set to zero for all analyses.

7. General Statistical Considerations

All data will be presented in data listings. Data from subjects excluded from an analysis population will be presented in the data listings, but not included in the calculation of summary statistics. Demographic and baseline characteristics will be summarized overall and by treatment for all subjects.

7.1 Subject Disposition

The number of subjects who enroll in the study and the number and percentage of subjects who complete each assessment will be presented. The frequency and percentage of subjects who withdraw or discontinue from the study and the reason for withdrawal or discontinuation will be summarized.

7.2 Demographic and Baseline Characteristics

Continuous demographic and baseline characteristic variables (age, height, weight, and body mass index) will be summarized overall and by treatment using descriptive statistics (number of subjects, mean, standard deviation [SD], median, minimum, and maximum). The number and percentage of subjects in each class of categorical demographic and baseline characteristic variables will also be summarized.

7.3 Pharmacokinetic Analyses

7.3.1 Naloxone Concentration Comparisons

The primary endpoint is the first timepoint when there is a higher naloxone plasma concentration in the 4-dose naloxone arms compared to the 2-dose naloxone arm. Separate comparisons will be performed with the 4-dose naloxone arm A (test) versus the 2-dose naloxone arm C (reference) and the 4-dose naloxone arm B (test) versus the 2-dose naloxone arm C (reference). No adjustment for multiplicity is planned for these separate comparisons.

Secondary endpoints will include determination of the first time point when there is a higher naloxone plasma concentration in the 4-dose naloxone arm B (2 doses every 2.5 minutes) as test compared to the 4-dose naloxone arm A (1 dose every 2.5 minutes) as reference. The same approach outlined for the primary endpoint analysis above will be used for this secondary endpoint comparison. The secondary endpoint analysis will be conducted regardless of the primary endpoint results.

Table 7-1: Pre-specified Timepoints and p -value Threshold for Comparing Naloxone Concentrations Across Treatments (Maintain Overall p -value Per Comparison at 0.05) (Pocock, 1977)

Comparison	Time (min)	Interim Analysis	p -value Threshold
Treatment A vs Treatment C (primary)	10	1	0.0221
	12.5	2	0.0221
	15	3 (final)	0.0221
Treatment B vs Treatment C (primary)	4.5	1	0.0221
	7	2	0.0221
	10	3 (final)	0.0221
Treatment B vs Treatment A (secondary)	4.5	1	0.0221
	7	2	0.0221
	10	3 (final)	0.0221

For both the primary and secondary analyses, up to three different time points have been pre-specified for each comparison. Time points will be evaluated from earliest to latest time (Table 7-1). Testing will be conducted sequentially along planned interim analyses (i.e., start at the initial time and progress forward, stopping if success is achieved) at a 0.0221 significance level. Testing will proceed through each time point until either one passes (reported as the earliest time where a difference in concentration is observed) or all pre-specified time points fail (no difference in naloxone concentrations between treatments for the selected time points).

For comparing treatment A to treatment C, the analysis will use naloxone concentration data collected at 10, 12.5, and 15 min. For both the treatment B to treatment C comparison and the treatment B to treatment A comparison, the pre-specified time points are 4.5, 7, and 10 min. All

subjects contributing naloxone concentration measures from both treatments at the pre-specified time points will be included in the analysis. At each of these timepoints, subject-level naloxone concentration will be log-transformed. Naloxone concentration values that are below the lower limit of quantification (i.e., zero) will result in that time point from that subject being removed for comparisons involving that treatment arm.

A paired Student's t-test will be used for comparing naloxone concentrations between treatments. To demonstrate an increase in naloxone concentration with the test compared to reference, it is necessary that the lower bound of the one-sided 97.79% interval for the geometric mean ratio excludes 1. The results will be transformed back to the original scale by exponentiation to provide treatment geometric means.

Normality assumption will be verified using the Shapiro-Wilke test for normality and homogeneity of variances will be verified using Levene's test. If either assumption is not valid, a Mann-Whitney-U test will be used for the comparisons rather than a t-test.

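### When all three one-sided tests for an increase fail, the SAP's pre-specified conclusion is no difference, which those tests cannot support

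*SAP*

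**What the plan says.** SAP 7.3.1 covers two primary comparisons (A versus C, B versus C) and one secondary comparison (B versus A). Each has three time points, tested from earliest to latest at 0.0221. The first success is reported as the earliest time of a difference. If none succeeds, the stated outcome is "no difference in naloxone concentrations between treatments for the selected time points".

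The method is given in the same section: "A paired Student's t-test will be used for comparing naloxone concentrations between treatments". For success, "it is necessary that the lower bound of the one-sided 97.79% interval for the geometric mean ratio excludes 1". SAP 4.4 plans on the same basis, with "power at a 0.0221 significance level for a one sided, log-transformed paired comparison (for the primary endpoint".

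For these concentration comparisons the SAP sets no equivalence margin, no upper confidence bound, no two-sided interval on the ratio and no test for a decrease. Protocol 4.9.5 does not say how a failed sequence is to be reported, and Protocol 4.9.1 (Analysis Populations) lets the SAP prevail where the two differ.

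**The concern.** A one-sided test for an increase has two possible results: an increase is shown, or it is not. The second covers a true ratio of 1, a modest increase that 18 pairs could not detect, and a decrease. The SAP gives all three the same label, and the label asserts the first.

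This bears on the question the study asks. The protocol's background says that close spacing and re-dosing a nostril may make the rise in concentration less than dose-proportional, or delay it. A small or late rise is the case most likely to fail at 4.5 to 15 minutes. A reader of the report could then conclude that extra or faster doses add nothing early on, when the data had only failed to show that they do. The rule governs the primary endpoint and the first secondary endpoint.

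**Working it through.** **Inputs.** Ratios, CVs and power come from SAP Table 4-1 and the one-sided 0.0221 threshold from SAP 7.3.1. The number of pairs is 18 (Table 4-1; Protocol 4.9.1: "These power calculations are based on 18 subjects with each comparison, allowing for potential dropouts"). The correlation between time points is not in the documents, so 0, 0.5, 0.8 and 0.95 were assumed.

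**Step 1: reproduce Table 4-1.** Take the SD of the paired log difference as s = √ln(1 + CV²). Power is the probability that a noncentral t with 17 df and noncentrality δ = ln(ratio) × √18 / s exceeds the critical value 2.173. For A versus C at 10 minutes (CV 68%, ratio 1.36):

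- s = √ln(1 + 0.68²) = 0.6165
- δ = 0.3075 × 4.243 / 0.6165 = 2.116
- power = 49.1%, against 49 in the table

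| Comparison | Recomputed power (%) | Table 4-1 (%) |
|---|---|---|
| A vs C at 10, 12.5, 15 min | 49.1, 90.7, 99.9 | 49, 91, 100 |
| B vs C at 4.5, 7, 10 min | 85.8, 94.2, 99.3 | 86, 94, 99 |
| B vs A at 4.5, 7, 10 min | 85.8, 87.9, 68.4 | 86, 88, 68 |

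All nine cells agree, so this is the SAP's model.

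**Step 2: how often all three tests fail.** Paired log differences for 18 subjects were simulated at the three time points, with the CVs above, one common correlation and 60,000 trials per setting. The table gives the percentage of trials in which all three tests fail, across the four correlations.

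| True ratio | A vs C | B vs C | B vs A |
|---|---|---|---|
| As planned in Table 4-1 | about 0.1 or less | under 1 | 0.5–10 |
| Constant 1.3 (assumption) | 13–38 | 37–61 | 37–61 |
| Constant 1.5 (assumption) | 0.3–6 | 7–27 | 7–27 |
| Constant 2 | about 0 | under 1 | under 1 |
| Constant 0.7 (assumption) | about 100 | about 100 | about 100 |

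Hand check for planned B versus A at zero correlation: (1 − 0.858) × (1 − 0.879) × (1 − 0.684) = 0.142 × 0.121 × 0.316 = 0.0054, or 0.5%.

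**Step 3: what a failed test leaves open at one time point.** The two-sided interval matching a one-sided 0.0221 test has level 1 − 2 × 0.0221 = 95.58%. Its half-width on the log scale is h = 2.173 × s / √18. At CV 68%, h = 2.173 × 0.6165 / 4.243 = 0.316. An observed ratio of exactly 1 then gives exp(±0.316) = 0.73 to 1.37. A test that only just fails has upper limit exp(2 × 0.316) = 1.88. This takes the observed SD as equal to the planned one.

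| CV (%) | Interval if observed ratio is 1 | Upper limit if test just fails |
|---|---|---|
| 48 | 0.79–1.26 | 1.59 |
| 58 | 0.76–1.32 | 1.74 |
| 68 | 0.73–1.37 | 1.88 |
| 90 | 0.67–1.48 | 2.20 |
| 111 | 0.63–1.58 | 2.50 |

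Even an observed ratio of 1 does not exclude an increase of about a quarter to a half, or a decrease of 20% or more.

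**The case against.** The strongest defence is that the phrase is a parenthesis closing a sequential algorithm. It is limited to the selected time points, and the next paragraph makes clear that the test exists to demonstrate an increase. The SAP makes no equivalence claim, and under its planning assumptions the primary comparisons almost never reach this branch. Other planned outputs also guard against a misreading: treatment geometric means, concentration-time profiles, six partial AUCs up to 30 minutes, ratios with 90% intervals for Cmax and AUC, and the rescue-time modelling.

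Much of this stands. The data are not hidden. But none of these outputs gives an interval on the ratio at the tested time points, and the parenthesis is the only pre-specified description of the failing outcome, so it may pass straight into the report.

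Two stronger readings are tempting and should not be drawn:

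- **That the rule would readily miss a true 2-fold increase.** On the SAP's own inputs, a 2-fold increase at all three time points fails every test in under 1% of trials. Ratios near 2 matter only at a single time point, in the early part of the B versus A pattern, or if the CVs are larger than planned.
- **That the protocol foresees the test arm falling below the reference.** It names only a less than dose-proportional or delayed increase. Treatment A gives C's two doses at the same times and in the same nostrils, then adds two more. The 0.7 scenario shows what the label would cover; it is not an expectation taken from the documents.

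**Conclusion.** The point holds as an error in a pre-specified conclusion; the design is not at fault. Failure of three one-sided tests supports saying that an increase was not demonstrated, and nothing further.

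The practical exposure is to modest increases, with 37–61% failure for either comparison involving B at a constant 1.3-fold, and to the secondary B versus A comparison, where even the planned pattern fails in up to about 10% of trials. These figures rest on 18 complete pairs, the Table 4-1 CVs and the assumed correlations. The SAP itself allows that its CVs may be too low, and it drops unquantifiable and out-of-window samples. Larger CVs or fewer pairs would raise the failure rates for a true increase. The logical fault depends on none of these assumptions.

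**What to change.** In SAP 7.3.1, replace the parenthesis with: *an increase was not demonstrated at the pre-specified time points*.

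Add that the geometric mean ratio will be reported with a two-sided interval at each pre-specified time point for all three comparisons. A level of 95.58% would match the one-sided 0.0221 threshold. Because testing stops at the first success, intervals at later time points are additional analyses and should be labelled descriptive. Keep any statement of no difference for a pre-set equivalence bound, should one be wanted.

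The cost is one changed phrase, a short addition and at most 3 × 3 = 9 intervals from concentrations already being collected. Alpha, sample size, sampling times and the stopping rule do not change.

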3.1 Study Design

This study will be a randomized, unblinded, three-way crossover study to determine naloxone plasma concentration after administration of multiple doses of intranasal (IN) naloxone.

Table 3-1: Study Schedule

Day -1	Day 1	Days 2-3	Day 4	Days 5-6	Day 7	Day 8
Check-in	Treatment Period 1	Washout	Treatment Period 2	Washout	Treatment Period 3	Check-out

The following 3 treatments will be evaluated in a randomized order over the 3 treatment periods.

Table 3-2: Study Treatments

Treatment	Description
A	Four 4 mg IN naloxone doses (1 dose every 2.5 min; L at 0 min, R at 2.5 min, L at 5 min, R at 7.5 min)
B	Four 4 mg IN naloxone doses (2 doses every 2.5 min; L and R at 0* min, L and R at 2.5* min)
C	Two 4 mg IN naloxone doses (L at 0 min, R at 2.5 min)

*L = Left Nostril, R = Right Nostril, * doses will be ~5 seconds apart (one after the other)*

Healthy subjects will be randomized to one of six treatment sequences (i.e., ABC, ACB, BAC, BCA, CAB, CBA). FDA will prepare the randomization schedule. Subjects will report to the study site for screening from Days -28 to -2 and then will return to the site on Day -1 for baseline assessments and check-in. After check-in (Day -1), subjects will receive dosing for the 3 respective treatment periods on Days 1, 4 and 7. There will be two days of washout between each treatment period. Participants will be confined in the study clinic from Day -1 until the morning of Day 8. On dosing days, dosing will occur as per the treatment description and PK assessments will occur at the following time points:

- PK assessment: 0 (pre-dose), 2, 4.5, 7, 10, 12.5, 15, 20, 30, 45, 60, 120, 180, 240, 360, and 720 minutes

The subject should remain fully supine for approximately one-hour post-dose. Subjects should be instructed not to breathe through the nose during administration of the nasal spray into the nose. Subjects will be instructed to leave their masks off for twenty minutes after drug administration.

A summary of all assessments prior to and following study drug administration on Day 1, is described in the Protocol, Schedule of Events.

Subjects will be discharged from the study after completion of all study procedures. If a subject discontinues from the study prematurely, all procedures scheduled for the end of the study will be performed.

4. Study Endpoints

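### The primary A vs C test leaves out the 4.5-min sample, drawn while A and C dosing is still identical; adjusting for it is a cheap efficiency gain whose size depends on a correlation the documents do not give

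*SAP*

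**What the plan says.** For the first primary comparison, SAP 7.3.1 states that "the analysis will use naloxone concentration data collected at 10, 12.5, and 15 min". Times are tested in that order, each at 0.0221, and testing stops at the first success, which is reported as the earliest time with a difference. The method is a paired Student's "t-test will be used for comparing naloxone concentrations between treatments", applied to log concentrations with no covariate.

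SAP 3.1 (Table 3-2) gives Treatment A as "L at 0 min, R at 2.5 min, L at 5 min, R at 7.5 min" and Treatment C as "Two 4 mg IN naloxone doses (L at 0 min, R at 2.5 min". The same section schedules a PK sample at 4.5 min in every period.

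SAP 4.4 sizes the trial so that at least one planned time has "greater than 90% power at a 0.0221 significance level for a one sided, log-transformed paired comparison". It says that "the power for the 4-dose naloxone arm A (test) versus the 2-dose naloxone arm C (reference) was expected to be lower" than for B vs C. The Table 4-1 row for the earliest A vs C test, in the order time, ratio, CV and power, reads "Treatment A vs Treatment C 10 1.36 68 49". Protocol 4.9.1 adds: "These power calculations are based on 18 subjects with each comparison, allowing for potential dropouts".

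**The concern.** Up to 4.5 min a subject on A and the same subject on C have received the same two sprays at the same times. Table 4-1 agrees: B/C and B/A are both 2 at 4.5 min, so A/C = 2/2 = 1. Any A-C difference seen at 4.5 min is occasion-to-occasion noise, such as spray delivery and early absorption on the day. If that noise carries forward to 10 min, the unadjusted test leaves it in the error term although a measurement of it is already in hand.

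The endpoint is the first time with a difference, and 10 min is the first A vs C time tested. At 49% power, the plan's own assumptions give about an even chance of missing a true difference at 10 min and moving on to 12.5 min or later.

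**Working it through.** **Inputs.** n = 18 pairs (Protocol 4.9.1; Table 4-1). Ratio 1.36 and CV 68% at 10 min, one-sided 0.0221 (SAP 4.4). r is the correlation between a subject's A-C log difference at 4.5 min and at 10 min. It is not in the documents, so a range of 0 to 0.8 is assumed.

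**Step 1: reproduce the planned power.**
- Effect: ln(1.36) = 0.3075.
- SD of the paired log difference: sqrt(ln(1 + 0.68²)) = 0.6165.
- Noncentrality: 0.3075 × sqrt(18) / 0.6165 = 2.116.
- Critical value, t with 17 df at one-sided 0.0221: 2.173.
- Power from the noncentral t: 49.1%, against 49% stated.

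The same formula gives 90.7% at 12.5 min and 99.9% at 15 min (stated 91% and 100%). It also reproduces the other six powers in Table 4-1.

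**Step 2: power of the adjusted test at 10 min.** Regress the log difference at 10 min on the log difference at 4.5 min and test the intercept. The residual SD is 0.6165 × sqrt(1 − r²). Estimating the slope inflates the variance by about 1 + 1/(n − 3) = 1 + 1/15 = 1.067. The df are n − 2 = 16, with critical value 2.184.

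At r = 0.6 the residual SD is 0.6165 × 0.8 = 0.493, the standard error is 0.493 × sqrt(1.067) / sqrt(18) = 0.120, and the noncentrality is 0.3075 / 0.120 = 2.56.

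| r | Noncentrality | Power |
|---|---|---|
| 0 | 2.05 | 46% |
| 0.25 | 2.12 | 49% |
| 0.3 | 2.15 | 50% |
| 0.5 | 2.37 | 58% |
| 0.6 | 2.56 | 65% |
| 0.7 | 2.87 | 75% |
| 0.8 | 3.41 | 88% |

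Break-even is where (1 − r²)(1 + 1/15) = 1, that is r² = 1/16, r = 0.25. Simulation agrees with the table to within about half a point.

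**Step 3: validity of each test.** Simulated one-sided type I error of the intercept test at n = 18 is 0.021 to 0.023. The effect must be read at a covariate difference of zero. If the covariate is centred at its sample mean, the standard error is too small, and simulated type I error is about 0.05 at r = 0.6 and 0.10 at r = 0.8.

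**Step 4: incomplete covariates.** Dropping incomplete pairs is costly: with 16 pairs, power is 59% at r = 0.6 and 83% at r = 0.8; with 14 pairs, 51% and 76%. If instead all 18 pairs are kept and 2 to 4 covariate differences, chosen at random, are set to zero, power is about 60-63% at r = 0.6 and 75-82% at r = 0.8. Type I error stays near 0.022.

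**Step 5: overall error over the three times.** Removing a shared baseline lowers the correlation among the 10, 12.5 and 15 min tests. In simulations under assumed correlations, overall one-sided error rose from between 0.039 and 0.050 without adjustment to between 0.046 and 0.059 with it. Whatever the correlation, it cannot exceed 3 × 0.0221 = 0.0663.

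**The case against.** The strongest objection is that nothing here is broken. A paired t-test on log concentrations is valid. The plan discloses the 49%, says that A vs C is the weaker comparison, and meets its stated target at 12.5 min (91%) and 15 min (100%). All of that stands. A reader might infer that the A vs C comparison is underpowered or wrongly analysed; the SAP sets no power target for 10 min, so the documents do not support that.

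A reader might also infer that adjustment would raise power from 49% to 65-88%. That range holds only for r between 0.6 and 0.8. SAP 4.4 derives its variability from summary label data, which supply no correlation between times. By superposition, 1/1.36 = 74% of A's mean 10-min level comes from the first two sprays. That makes a useful r plausible, but it is a share of the mean, not of the variance of the A-C difference. The 4.5-min value is also the noisier one (CV 111% against 68%), which may lower r. A simulated absorption model can produce r of 0.6 to 0.8, but only with variance inputs that the documents do not contain.

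Three practical objections also stand:
- Setting a missing covariate to zero conflicts with the no-imputation rule in SAP 6.1 and Protocol 4.9.8. Zero is also only approximate when one period is below quantification and the other is not, because the sign is then known.
- The 0.0221 threshold was chosen for the unadjusted tests.
- The rank-test fallback has no place for a covariate.

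Each can be settled in the SAP text. None removes the reason to use the sample.

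**Conclusion.** The point holds as a low-cost improvement. The plan leaves unused a scheduled measurement that A's later sprays cannot affect, in the comparison where it has least power. Adjusted power at 10 min is about 46% to 88% for r from 0 to 0.8, against 49% planned. The trade is lopsided: at most about 3 points lost (49 − 46) if r is below about 0.25, and 39 gained (88 − 49) if r reaches 0.8.

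The result rests on the Table 4-1 ratio and CV, on 18 pairs with approximately normal log differences, on an assumed r, and on 4.5-min samples drawn before A's third spray. The practical consequence is a possibly better chance of reporting 10 min rather than a later time. The validity of the planned test is not in question.

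**What to change.** In SAP 7.3.1, for A vs C only, and before any concentration data are available:

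1. Regress each subject's log(A/C) at the tested time on the same subject's log(A/C) at 4.5 min. Test the uncentred intercept one-sided with n − 2 df, and report its exponential as the geometric mean ratio.
2. Use a 4.5-min sample only if it was drawn before A's actual third spray. The ±0.5 min window reaches 5.0 min, the nominal time of that spray.
3. If the covariate is missing or below quantification in either period, set its difference to zero. State this as an exception to the no-imputation rule in SAP 6.1, for the covariate only.
4. Apply the normality check to the regression residuals and leave the rank fallback unadjusted.
5. Keep the plain paired t-test as a sensitivity analysis.
6. Confirm by simulation, over a stated range of correlations, that 0.0221 at each of the three times holds overall error at 0.05. If it does not, tighten the threshold slightly.

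The cost is some SAP text, a little code and one simulation, with no new samples. The statistical price is one degree of freedom and the small power loss at low r. A vs C would also be analysed differently from the two B comparisons, where dosing differs from the first spray and no such baseline exists.
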